6.8.1.4 Subgroup analyses

The protocol does not plan any analysis by subgroup, however the study treatment effect across the following subgroups will be explored by repeating the main analysis on primary PD endpoint, assuming there are enough subjects, i.e., ≥ 10 subjects by subgroup.

- Age: < 55 vs ≥ 55 years
- BMI: < 25.0 vs (≥ 25.0 and < 30.0) vs ≥ 30.0 kg/m²
- Sex: male vs female
- Diabetes mellitus at baseline: yes vs no

- Chronic kidney disease: yes vs no

PTs to consider for identification of subjects with/without diabetes mellitus, or chronic kidney disease, are described in Section 5.4.4.

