2.1 Study design

This is a prospective, multi-center, open-label, randomized, parallel-group, Phase 2, exploratory study of a single subcutaneous (s.c.) administration of ACT-246475, at two different dose levels, in subjects with acute myocardial infarction (AMI; ST-segment elevation myocardial infarction [STEMI] or non-STEMI [NSTEMI]) scheduled for invasive strategy.

Approximately 42 adult subjects with confirmed diagnosis of AMI (STEMI or NSTEMI), with a time from onset of symptoms of more than 30 min and less than 6 hours, will be randomized to receive ACT-246475 at the dose of either 8 or 16 mg, in a 1:1 ratio, injected s.c. in the thigh in addition to standard of care / conventional treatment. Injection of ACT-246475 will be performed as soon as possible after randomization.

The study design is shown in [Figure 1](#).

Figure 1 Study design

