6.8.1 Primary pharmacodynamic endpoint

The study is designed to demonstrate that a single injection of ACT-246475 enables a large proportion (a target of 85%) of subjects to achieve a clinically meaningful level of inhibition of platelet aggregation (IPA), i.e., PRU < 100 at 30 minutes after study drug injection.

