6.8.1.2 Analysis

The analyses described in this section consider the primary endpoint, i.e., PD response. Sensitivity analysis of the PD endpoints will be described in Section 6.8.1.3.

Unless stated otherwise, all analyses will be conducted on the mFAS.

Hypotheses and statistical model

The primary objective is to assess IPA 30 min after a single s.c. injection of ACT-246475 in subjects with AMI receiving conventional antithrombotic treatment (e.g., aspirin, oral P2Y₁₂ receptor antagonists, anticoagulants).

To achieve this objective, the testing strategy will be to test the study treatment effect (using the proportion *p* of responders, i.e., achieving PRU < 100 at 30 minutes post-injection) for each of the two doses, considering the following hypotheses:

$$H_{0HD}: p_{HD} \leq 50\% \text{ vs } H_{1HD}: p_{HD} \geq 85\%$$

$$H_{0LD}: p_{LD} \leq 50\% \text{ vs } H_{1LD}: p_{LD} \geq 85\%$$

where LD is the lower ACT-246475 dose (8 mg), and HD the higher ACT-246475 dose (16 mg).

Each of the two null hypotheses will be tested by a two-sided z-test at a significance level (alpha) of 0.025, which is an overall level of 0.05 for the study level and adjusted for multiplicity using Bonferroni method.

Main analysis

The primary statistical analysis will be performed on the mFAS population for each dose level.

It will be based on the study treatment received (which may differ from the assigned one).

The analysis of the primary endpoint will be performed for each of the two doses independently, i.e., considering 2 null hypotheses (proportion of patients achieving a

response is less than or equal to 50%) at 0.025 type I error each [see protocol section 10.3.3.1].

The study will be declared positive for the primary objective, if at least 1 out of the 2 null hypotheses is rejected at 0.025 type I error level.

A one-sided z-test will be computed and the 95% CI of the proportion of responders will be provided.

A summary of response, in terms of number (%) of responding subjects, will be provided.

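### The subgroup rule in SAP 6.8.1.4 sets no minimum per dose, so the per-dose z-test against 50% may be run on about 4–5 subjects, where its p-value is too small (one-sided reading) or can never be significant (two-sided reading)

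*SAP*

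**What the plan says.** SAP 6.8.1.4 lists five factors (age, BMI, sex, diabetes, chronic kidney disease) and states that the effect across them "will be explored by repeating the main analysis on primary PD endpoint, assuming there are enough subjects". Enough is defined as "≥ 10 subjects by subgroup".

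The analysis to be repeated is in SAP 6.8.1.2: "The primary statistical analysis will be performed on the mFAS population for each dose level". Each dose is tested against a null responder proportion of at most 50%. The section describes the test in two ways. Under the hypotheses: "Each of the two null hypotheses will be tested by a two-sided z-test at a significance level (alpha) of 0.025". Under the main analysis: "A one-sided z-test will be computed and the 95% CI of the proportion of responders will be provided". No exact test, continuity correction or interval method is named.

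Allocation is equal (SAP 2.1): subjects "will be randomized to receive ACT-246475 at the dose of either 8 or 16 mg, in a 1:1 ratio".

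**The concern.** The size rule is worded by subgroup, but the test is run by dose. A subgroup that only just qualifies can therefore be cut roughly in half before testing. With four or five subjects the normal approximation to the binomial is poor, and the p-value printed for the cell may not mean what it says.

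At stake is how the subgroup table is read. A cell of four responders out of four could be marked significant at one dose, beside a non-significant cell at the other dose or in another subgroup level, although the data cannot support that contrast. Protocol 3.2 and 4.2 say that the study's results will help to select the Phase 3 dose, so a misleading subgroup table would have readers.

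**Working it through.** **Inputs.** Null 50%, target 85%, 0.025 per dose (SAP 6.8.1 and 6.8.1.2); power 90% and 21 evaluable per arm, 42 in total (Protocol 10.5); subgroup minimum 10 (SAP 6.8.1.4); 1:1 allocation (SAP 2.1).

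**1. Which z-test.** The documents do not give the variance form, so I inferred it from the sample size:

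n = [(z_α·√(0.5·0.5) + z_0.90·√(0.85·0.15)) / 0.35]²

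- Two-sided 0.025, null variance: [(2.2414·0.5 + 1.2816·0.3571)/0.35]² = 20.34, rounded up to **21**, the planned figure.
- One-sided 0.025, null variance: 16.87, rounded up to 17.
- Variance under the alternative throughout: 13 (two-sided) or 11 (one-sided).

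Only the first reproduces 21. I therefore use z = (x/n − 0.5)/√(0.25/n).

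**2. Cell sizes at the threshold.** Take 10 as the total over both doses and draw the 10 at random from 21 + 21 subjects. The split is 5/5 with probability 28% and 4/6 with probability 44%. The smaller cell thus has 4 or 5 subjects in about 72% of cases and 3 or fewer in about 28%.

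**3. Test behaviour when all subjects respond.** Here z = 0.5/√(0.25/n) = √n, and the exact one-sided p is 0.5^n. Critical values are 1.960 (one-sided 0.025) and 2.241 (two-sided 0.025).

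| Responders | z | One-sided p | Exact one-sided p | Two-sided p | One-sided 0.025 | Two-sided 0.025 |
|---|---|---|---|---|---|---|
| 3/3 | 1.732 | 0.042 | 0.125 | 0.083 | no | no |
| 4/4 | 2.000 | 0.023 | 0.0625 | 0.0455 | rejects | no |
| 5/5 | 2.236 | 0.013 | 0.031 | 0.0253 | rejects | no |
| 6/6 | 2.449 | 0.007 | 0.0156 | 0.0143 | rejects | rejects |

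One non-responder removes the rejection at n = 4 or 5: 3/4 gives z = 1.00 and 4/5 gives 0.3/0.2236 = 1.34. The true one-sided size is therefore 6.25% at n = 4 and 3.1% at n = 5, against 2.5% nominal. The two-sided version has no rejection region for n ≤ 5. An exact one-sided test at 0.025 cannot reject before 6/6 either.

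**4. Is this outcome rare?** At the 85% target, all subjects respond with probability 0.85⁴ = 52% for n = 4 and 0.85⁵ = 44% for n = 5. It is not.

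**5. Other forms of the test.** With a continuity correction, z = 1.50 at 4/4 and 1.79 at 5/5, and neither version rejects. With the sample variance, the standard error is zero when all respond and z is undefined.

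**6. How many tests.** There are 2 + 3 + 2 + 2 + 2 = 11 subgroup levels, and 11 × 2 doses = 22 tests at most. With complete data, the larger level of each two-level factor holds at least 21 of the 42 subjects, an average of at least 10.5 per dose. That is 4 levels, or 8 of the 22 tests, where cells of 4–5 are not to be expected.

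**The case against.** The strongest reply is that the 10 may be meant per dose. The condition directly follows the reference to an analysis that is itself run per dose, and on that reading cells of 4–5 never arise. This stands as a possibility. The text does not say it, so the rule needs clarifying in any case.

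Four stronger readings are tempting, and the documents do not support them:

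- **That over-rejection and inability to reject occur together.** They belong to alternative descriptions of the test in SAP 6.8.1.2. Under the two-sided version, the one that matches n = 21, small cells produce no false positives, only uninformative results. The miss at 5/5 is also narrow (2.236 against 2.241).
- **That all 22 tests are defective.** That number is the maximum count. Small-cell failure needs a level close to the threshold. Remaining inaccuracy of the z-test in larger cells is a matter for the primary analysis.
- **That a confidence interval of 100% to 100% would be printed.** This requires a sample-variance interval, and the SAP names no method.
- **That subgroup p-values would decide the dose.** No section says so. Protocol 4.2 refers to this study's results together with those of ID-076A201.

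It is also fair that repeating the main analysis already yields responder counts and a 95% interval per dose, so the change is small. SAP 6.8.1.3 also plans a logistic regression with age and gender as covariates and a STEMI/NSTEMI-by-dose interaction test, so the plan does not rely on separate cell tests alone. Formal differences between levels would be very imprecise here and are a matter of preference.

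**Conclusion.** The point holds as a minor defect of specification. As written, the rule allows a z-test on about 4–5 subjects per dose. The one-sided version then prints 0.023 where the exact value is 0.0625 (4/4), and 0.013 where it is 0.031 (5/5). The two-sided version cannot reject at all with 5 or fewer subjects.

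This rests on three assumptions: the 10 is the total over both doses; z uses the null variance; there is no continuity correction. The first is the natural reading but not the only one. The second is inferred from the sample size. The third follows from the SAP's silence.

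The consequence is limited. The subgroup analyses are exploratory, only small cells are affected, and nothing here changes whether the study is declared positive.

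**What to change.** In SAP 6.8.1.4:

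1. Replace the repeated z-test by responders/n with exact (Clopper-Pearson) 95% confidence intervals for each dose, without p-values. For 5/5 the lower limit is 0.025^(1/5) = 0.478, so the interval is 48% to 100%, which shows plainly how little such a cell can say. SAP 6.8.2.4 already plans only descriptive summaries of the other PD endpoints in these subgroups.
2. State that the minimum of 10 applies to each dose-by-subgroup cell.

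Optionally, add differences between subgroup levels with confidence intervals, described as imprecise. This is not needed to correct the problem.

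The cost is SAP wording, with no new data and no change in sample size. Subgroup p-values are lost, and fewer cells are reported. In an arm of 21, both levels of a two-level factor reach 10 only if they split 10/11, and at most two of the three BMI levels can (3 × 10 = 30 exceeds 21). Because exact intervals are valid at any size, the minimum then serves presentation rather than validity.

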6.8.2 Other pharmacodynamic endpoints analysis

Unless stated otherwise, all analyses will be conducted on the FAS.

6.8.2.1 Variables

Endpoints

Other PD endpoints are the following:

- *PD profile over time* based on absolute PRU values at 15, 30 and 60 minutes post dose,
- *PRU_{60m} status*: PRU status (value < 100) at the 60 minutes post dose time point.

Variables

The *PD profile over time* variable will be based on actual PRU values reported at 15, 30 and 60 minutes after study drug injection.

The *PRU_{60m}* variable is the actual P2Y₁₂ reaction unit value as reported by VerifyNow®, at 60 min after study drug injection.

6.8.2.2 Analyses

Summary statistics will be provided for the PD endpoint variable *PRU_{60m} status*, and individual data will be listed. It will be analyzed similarly to the primary PD endpoint in Section 6.8.1.2, and will use the same factors.

A longitudinal analysis of the study treatment effect, on *PD profile over time* will be performed using a mixed model with PRU as the dependent variable, subject as a random factor, and study treatment (ACT-246475 8 mg, and ACT-246475 16 mg), PRU level at baseline, time from onset of symptoms to study treatment administration (continuous, hours), age (continuous), sex (male, female), and assessment time (15, 30 and 60 minutes) as fixed factors.

The proportion of subjects with PRU < 100 by assessment time (0 to 60 minutes) will be plotted as bar charts.

Descriptive statistics of PRU relative change from baseline at each time point will be provided, where change from baseline is defined as the ratio of $([PRU \text{ at time } t - PRU \text{ pre-dose}] / PRU \text{ pre-dose})$ expressed in percentage.

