### 1.3 Purpose and rationale of the study

ACT-246475 is a potent, short-acting, reversible, and selective antagonist of the platelet P2Y12 receptor to be administered subcutaneously. ACT-246475 has shown a favorable PK/PD and safety profile in animal models, confirmed in studies conducted in healthy subjects. This Phase 2 study is complementary to study ID-076A201, which is being conducted in patients with stable coronary artery disease (CAD) to assess the PD, PK, tolerability and safety of a single s.c. injection of ACT-246475. AMI may be associated with sympathetic activation and subsequent peripheral vasoconstriction which might affect the uptake of ACT-246475 after s.c. administration and consequently its onset of action. This study will generate complementary data to assess whether the onset of action of ACT-246475 is affected in a population of patients with AMI. The impact of the 2 different doses on the PD and PK of ACT-246475 when administered on top of standard of care for AMI (e.g., antiplatelet and anticoagulant therapies) will be assessed in this study. The two doses will be the same as the ones evaluated in study ID-076A201.

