6.8.2.3 Supportive/sensitivity analyses

Not applicable.

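### The PRU-over-time model in SAP 6.8.2.2 implies equal variance and equal correlation at 15, 30 and 60 min, so its intervals for time-specific means and between-time differences are likely to be miscalibrated, in a direction the documents do not settle

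*SAP*

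**What the plan says.** SAP 6.8.2.1 places the PRU profile under the lead-in "Other PD endpoints are the following" and defines it as "based on absolute PRU values at 15, 30 and 60 minutes post dose". SAP 6.8.2.2 analyses it longitudinally, "performed using a mixed model with PRU as the dependent variable, subject as a random factor". The fixed part lists treatment, baseline PRU, time from symptom onset to dosing, age and sex, "and assessment time (15, 30 and 60 minutes) as fixed factors". All terms are additive: there is no treatment-by-time and no baseline-by-time term.

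No residual or repeated-measures covariance is named, and no robust standard error. SAP 6.8.2.3 marks sensitivity analyses for these endpoints as not applicable, and SAP sections 8 and 11 add no covariance rule. SAP 6.8.2 runs the model on the FAS and SAP 6.8.3 plans no imputation, so partial profiles would enter it.

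**The concern.** A random subject intercept with independent residuals allows one total variance and one within-subject correlation. Over this hour PRU is expected to drop from its pre-dose level toward zero. SAP 6.8.1 aims for "a large proportion (a target of 85%) of subjects to achieve a clinically meaningful level of inhibition of platelet aggregation", meaning PRU below 100 at 30 min. Protocol 1.3 adds that AMI may cause peripheral vasoconstriction, "which might affect the uptake of ACT-246475 after s.c. administration and consequently its onset of action". A bounded decline with patient-to-patient differences in speed will usually give spread that changes over time, and readings 45 minutes apart that correlate less than neighbouring ones. The model also holds the baseline-PRU slope constant across the three times.

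At stake are the model-based means at each time and the differences between times. The trial's title asks about onset of inhibition, and this is the only planned model that uses all three times together. Its by-time intervals could therefore look more, or less, certain than the data justify.

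**Working it through.** **Plan's own figure.** The documents give no figure for this model. The stated 21 per arm is for the primary responder test. It reproduces with the null-variance z-test at two-sided 0.025 and 90% power: n = [(2.241 × 0.5 + 1.282 × √(0.85 × 0.15)) / 0.35]² = 20.3, rounded up to 21. It serves below only as the number of subjects.

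**Inputs.** From the documents: 21 per arm, 1:1 allocation, times 15, 30 and 60 min, and the model terms. Assumed, because the documents are silent: PRU SDs and correlations.

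**Formulas.** With complete balanced data the fitted subject variance σ_b² averages the three true covariances, and σ_e² is the mean true variance minus that average. The ratio of model SE to true SE is then:
- mean at time t, both arms together: √(mean variance / Var_t)
- difference between times s and t: √(2σ_e² / (Var_s + Var_t − 2Cov_st))

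**Worked case.** SDs 90/70/50; correlations 0.7 (15–30), 0.7 (30–60), 0.5 (15–60).
- Mean variance = (8100 + 4900 + 2500)/3 = 5166.7
- Mean covariance = (4410 + 2450 + 2250)/3 = 3036.7, so σ_e² = 2130
- 15 min: √(5166.7/8100) = 0.80. 60 min: √(5166.7/2500) = 1.44
- 15 versus 60 min: √(4260/6100) = 0.84
- Dose contrast: the model uses σ_b² + σ_e²/3 = 3746.7; the true variance of a subject's mean is (15500 + 2 × 9110)/9 = 3746.7. They agree, so this interval is valid.

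**Coverage of nominal 95% intervals** (40,000 simulated trials per row; treatment, time and random subject only; correlations 0.7/0.7/0.5 unless noted; means over both arms):

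| SD at 15/30/60 | 15 min | 30 min | 60 min | 15 vs 60 | Dose contrast |
|---|---|---|---|---|---|
| 90/70/50 | 88.7% | 95.8% | 99.5% | 89.8% | 94.9% |
| 50/70/90 | 99.5% | 95.7% | 89.1% | 89.8% | 95.0% |
| 60/90/60 | 98.1% | 88.5% | 98.1% | 95.8% | 95.1% |
| 70/70/70 | 95.2% | 95.3% | 95.3% | 90.6% | 95.0% |
| 70/70/70, all correlations 0.6 | 95.2% | 95.1% | 95.2% | 95.0% | 95.1% |

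For fitted means within one arm the errors are milder: 91.4%, 95.4% and 98.0% in the first row.

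**Onset models.** Assumed pre-dose PRU 220 (SD 40), exponential fall with a log-normal rate, 21 per arm, adjusted for baseline PRU, 4,000 trials:

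| Share with PRU < 100 at 30 min | 15 min coverage | 60 min coverage |
|---|---|---|
| about 86% | 89–92% | about 99% |
| about 52% | 96–97% | about 94% |
| about 31% | 98% | 92% |

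A wider grid of 192 onset models varied pre-dose PRU (180–260), its SD (40–60), rate spread, absorption lag and assay error. After baseline adjustment, the SD at 15 min exceeded that at 60 min in 188 of 192 models at 85% response and 170 of 192 at 70%. At 50% response the order reversed in 132 of 192. At 85% the median model/true SE ratios were 0.82 at 15 min and 1.45 at 60 min.

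The 15–60 min correlation was the lowest of the three in every onset run. The model SE for the 15-versus-60 min difference was about 16–24% too small in the onset scenarios checked. Where an unstructured covariance was fitted to simulated complete data (unadjusted for baseline), coverage was 93–95.5% throughout.

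**The case against.** **Direction.** A reader might infer that the 15-min interval is simply too narrow and the 60-min interval too wide. The documents do not support that as fact, since they give no PRU SDs. It follows in onset models tuned to the 85% target, but it weakens near the 50% null rate and reverses when onset is slow, which is the situation Protocol 1.3 raises. This objection stands.

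**What the model is for.** SAP 6.8.2.2 introduces the model to assess the treatment effect, and the additive form yields one dose contrast common to all times. That contrast keeps its coverage with complete data. A reader might infer that dose comparisons at single times are distorted; as written the model produces none. The SAP also does not list by-time adjusted means or between-time differences as outputs. This stands, and it limits the point to quantities the model would readily supply but that are not named.

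**Other sources for by-time results.** SAP 6.8, 6.8.1.3 and 6.8.2.2 plan descriptive summaries at each time, with a confidence interval for the mean when relevant, and there is a separate PRU model at 30 min. Those summaries use each time's own variance, so a reader is not wholly dependent on this model. They do not supply an adjusted comparison between times.

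**Silence.** The SAP does not exclude a residual structure; it names none. That is fair, but the literal reading is the one a programmer would implement.

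**Simulation limits.** Age, sex and time from onset were omitted throughout, and baseline PRU in some runs. The effect of partial profiles was not quantified.

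**Conclusion.** The point holds as a low-priority one, worth considering rather than essential. Read literally, SAP 6.8.2.2 assumes compound symmetry, which an onset profile is unlikely to satisfy, and no planned analysis checks it. Intervals for time-specific means can be off either way: in the onset models, 15-min coverage ran from about 89% to 98% and 60-min coverage from about 92% to 99%, depending on how fast the drug acts. Under-coverage of the 15-versus-60 min difference is the steadier result. It appears in all onset models checked and even with equal SDs when correlation decays (90.6%), though not in the contrived pattern with spread peaking at 30 min (95.8%).

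All these sizes rest on assumed PRU distributions and, for coverage, on complete data. The overall dose contrast is sound under complete data. The primary responder test does not use this model, and the endpoint is an "other" PD endpoint in an exploratory study.

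**What to change.** In SAP 6.8.2.2, replace the random subject factor with a repeated-measures model: unstructured covariance across 15, 30 and 60 min within subject, Kenward-Roger degrees of freedom, and both treatment-by-time and baseline-PRU-by-time terms. Report the dose difference at each time and its equally weighted average. Name heterogeneous Toeplitz as the fallback if the model does not converge.

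The covariance and the treatment-by-time term should change together. With an unstructured covariance but one common dose effect, that effect becomes a weighted combination with erratic weights; in the checks the 30-min weight was negative (−0.25 to −1.3). With treatment-by-time but the present covariance, coverage of the dose difference under SDs 90/70/50 would be 88.9% at 15 min and 99.5% at 60 min.

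The cost is SAP wording and one changed model statement. The model would have six covariance parameters instead of two, plus two for treatment-by-time and two for baseline-by-time, and slightly fewer error degrees of freedom. That is affordable with about 42 subjects and three times.

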### 1.2.2.3 Study AC-076-102

This was a randomized, double-blind, placebo-controlled, SAD study to investigate the safety, tolerability, PK, and PD of ACT-246475 after s.c. (part A) and sublingual (s.l.; part B) administration to healthy male subjects.

In part A, there were a total of 48 subjects exposed (6 subjects receiving active treatment and 2 subjects receiving placebo per dose level).

ACT-246475 has been determined to be safe and tolerated at each s.c. dose level ranging from 1 mg to 32 mg.

The overall AE incidence was 12.5% (6 of 48 subjects exposed) without indication of dose dependency. There were 5 of 36 subjects with AEs after administration of ACT-246475 (13.9%) vs 1 of 12 after placebo (8.3%). Each AE after administration of ACT-246475 was mild and transient.

- In the 2 mg dose group, 2 subjects reported one AE each (headache; dizziness) after administration of ACT-246475.
- In the 8 mg dose group, there were 3 subjects with at least one AE after administration of ACT-246475 (rhinorrhea; headache; dizziness, nausea and hyperhidrosis)
- One subject reported 3 AEs after administration of placebo (catheter site erythema, nausea, and headache).
- In the other dose groups (1 mg, 4 mg, 16 mg, and 32 mg), no AEs were reported.

There were no deaths, SAEs, bleeding events, or AEs leading to discontinuation of the study. No clinically relevant changes in laboratory variables, vital signs, ECG variables, body weight, physical examination, or vigilance tests were observed.

Peak plasma concentrations were reached within approximately 30–45 min and  $t_{1/2}$  ranged from 1.3–9.2 h. Exposure essentially increased in a dose-proportional manner.

At each dose level, peak %IPA was achieved within approximately 15–30 min post-dosing. Peak %IPA exceeded 85% at doses  $\geq$  4 mg. The duration of PD effects was dose-dependent. At the two highest doses administered, mean %IPA  $\geq$  85% was

sustained for approximately 6 h and 12 h post-administration of 16 mg or 32 mg ACT-246475, respectively.

In part B, there were a total of 8 subjects exposed (6/2 on active/placebo). ACT-246475 has been determined to be safe and tolerated after a single s.l. dose of 20 mg. Two subjects reported AEs after s.l. administration of ACT-246475: lightheadedness in one subject and headache, vomiting, dizziness, and dyspepsia in the other subject. Neither of the two subjects exposed to placebo reported AEs.

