### 3.2 Study design rationale

The duration of the treatment period is justified by the primary objective, which is to characterize the onset of IPA after a single s.c. injection of ACT-246475 at two different doses in subjects with AMI.

The choice of the same two doses (i.e., 8 and 16 mg) as in the ongoing ID-076A201 study (see Section 5.1.1 for detailed rationale on dose selection), will provide supportive information for the selection of the dose to be tested in the Phase 3 pivotal study.

The IPA analysis will be performed with the VerifyNow® method. Results from VerifyNow® are well correlated with those obtained with the light transmission aggregometry (LTA) method [Varenhorst 2009, Gremmel 2015]. The VerifyNow® method has been preferred as it is more standardized than the LTA method and it is the method used for primary PD analysis in the ongoing ID-076A201 study in subjects with stable CAD. In addition, the volume of blood required per sample is higher for LTA (6 mL) than for the VerifyNow® method (3 mL). Accordingly, using the VerifyNow®

method will reduce the amount of blood collected for study purposes in a population with acute ischemic event.

The trial is conducted open-label to allow the investigator to adapt the standard AMI treatments to an individual subject's needs (e.g., antiplatelet and anticoagulant treatment). In addition, the primary endpoint being a pharmacological readout (P2Y12 reaction units [PRU] value at 30 min) with no room for data interpretation, the open-label design is fully justified. Because of the limited sample size and the absence of a placebo group, the presentation of the safety data will be purely descriptive.

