6.8.1.3 Supportive/sensitivity analyses

IPA as measured by VerifyNow® will also be summarized as a continuous variable.

Those summaries will be provided considering the available PD assessment time points (baseline, 15, 30, and 60 min post dose).

A mixed model to assess treatment effect at 30 min. from start of treatment injection on platelet reactivity as measured by VerifyNow®, i.e., PRU value, will be performed using subject as a random factor, and treatment (8 mg, and 16 mg), age (continuous), sex (male, female), and time from onset of symptoms to study treatment administration (continuous, hours), as fixed factors.

Assuming relevant number of subjects (i.e., ≥ 10 subjects) in each STEMI/NSTEMI subgroup, the consistency across STEMI and NSTEMI subgroups will be assessed by testing the interaction effect of STEMI/NSTEMI with study treatment dose in the primary endpoint analysis. Logistic regression analysis of the PD response will be performed using ACT-246475 dose (8 mg vs 16 mg), ST-segment elevation (STEMI vs NSTEMI), age (continuous), and gender (male vs female) as covariates.

The same analysis as described in the main analysis section will be performed on the additional PD response within the 1st hour endpoint using the FAS.

The main analysis, on the PD response, and PD response within the 1st hour, will be repeated on the PPS if the PPS is at least 10% smaller than the mFAS.

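### The PRU-over-time model gives one averaged dose difference; adding dose-by-time would give the 8 mg versus 16 mg contrast with a CI at 15 and 60 min as well (minor, supportive analyses only)

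*SAP*

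**What the plan says.** SAP 6.8.2.1 defines one of the other PD endpoints as the PRU profile at 15, 30 and 60 min. SAP 6.8.2.2 analyses it with a mixed model: subject random, and fixed factors treatment (8 mg, 16 mg), "PRU level at baseline, time from onset of symptoms to study treatment administration (continuous, hours), age (continuous), sex (male, female), and assessment time" at the three post-dose times. The list closes with "and assessment time (15, 30 and 60 minutes) as fixed factors". Dose and time enter as main effects, and no dose-by-time term appears there or elsewhere in the SAP.

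SAP 6.8.1.3 adds a separate model for one time point: "A mixed model to assess treatment effect at 30 min. from start of treatment injection on platelet reactivity". Its fixed factors are treatment, age, sex and time from symptom onset. Pre-dose PRU is not among them, although Protocol Table 2 schedules a pre-dose VerifyNow test and the 6.8.2.2 model adjusts for it.

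On purpose, Protocol 1.3 says that "The impact of the 2 different doses on the PD and PK of ACT-246475" will be assessed, and Protocol 3.2 describes the primary objective as one "which is to characterize the onset of IPA after a single s.c. injection of ACT-246475 at two different doses in subjects with AMI".

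**The concern.** A model with dose and time as main effects forces the two dose profiles to be parallel. Its one dose coefficient estimates the average of the differences at 15, 30 and 60 min. Its CI is right for that average but cannot be read as the difference at any single time.

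For an endpoint defined by its time course, the 15-min reading is the earliest information on onset. The other planned outputs do not fill the gap. SAP 6.8, 6.8.1.3 and 6.8.2.2 give by-dose summaries at each time, bar charts of the proportion below 100, and an analysis of 60-min responder status. At 30 min a dose contrast exists from 6.8.1.3. At 15 and 60 min no PRU contrast with a CI is planned.

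A smaller matter is that the two PRU models adjust differently for baseline, without a stated reason. That touches precision at 30 min only.

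At stake is how much the supportive dose comparison can say about timing.

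**Working it through.** **Inputs.** 21 evaluable subjects per arm comes from Protocol 10.5. The documents give no PRU standard deviation, correlation or expected dose gap, so the following are assumptions:
- normal PRU with SD 60 and no floor effect;
- correlation ρ = 0.4 to 0.8 between post-dose values;
- correlation r = 0 to 0.5 between pre-dose and post-dose PRU;
- pre-dose PRU in the model, as in SAP 6.8.2.2; age, sex and time from onset left out.

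The plan states no precision figure for these models, so there is none to reproduce.

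**Step 1: what the coefficient estimates.** With balanced data it is the mean of the three differences. For a gap (16 mg minus 8 mg) of −30, 0, 0 at 15, 30, 60 min, this is (−30 + 0 + 0)/3 = −10. As a check, 200 simulated trials with gaps of −60, −20 and −5 (mean −28.3) gave −28.9 from the main-effects model. The model with dose-by-time gave −61.2, −21.4 and −4.1.

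**Step 2: standard errors.**
- Averaged contrast: SE = 60 × √{[(1 + 2ρ)/3 − r²] × 2/21}
- Per-time contrast: SE = 60 × √{(1 − r²) × 2/21}

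**Step 3: coverage of the 15-min difference by the averaged CI.** For −30/0/0 the CI is centred 20 PRU from the 15-min value. Coverage is the probability that a noncentral t on 39 df, with noncentrality 20/SE, lies within ±2.023, allowing for chance baseline imbalance.

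| ρ | r | SE averaged | SE per time | Width ratio | Averaged CI covers 15-min value |
|---|---|---|---|---|---|
| 0.8 | 0 | 17.24 | 18.52 | 1.07 | 80% |
| 0.6 | 0.3 | 14.85 | 17.66 | 1.19 | 75% |
| 0.4 | 0 | 14.34 | 18.52 | 1.29 | 73% |
| 0.4 | 0.5 | 10.95 | 16.04 | 1.46 | 58% |

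Example, last row: (1 + 0.8)/3 − 0.25 = 0.35, so SE = 60 × √(0.35 × 2/21) = 10.95. Per time, 60 × √(0.75 × 2/21) = 16.04. The ratio is 1.46.

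Per-time CIs cover their own target in about 95% of trials. Smaller early gaps matter less: over the same range the averaged CI covers the 15-min value in about 78–88% for −20/0/0 and 86–91% for −15/0/0.

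**Step 4: chance of seeing an early gap.** For −30/0/0 the 15-min CI excludes zero in about 34–45% of trials, against about 8–14% for the averaged estimate. A 5% dose-by-time test has power of about 30–75% for −30/0/0, 15–40% for −20/0/0 and 10–25% for −15/0/0, so it should not decide what is reported.

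**Step 5: if the difference is constant.** Both models are unbiased with 94–96% coverage. Per-time CIs are then wider by the ratio in the table, about 7–46%.

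**Step 6: pre-dose PRU in the 30-min model.** The width ratio is close to √(1 − r²) × k. Here k is the cost of the extra term and of any subjects dropped for a missing pre-dose value. Simulated changes in 95% CI width at 42 subjects were:

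| Pre-dose values missing | r = 0 | 0.2 | 0.3 | 0.5 | 0.6 |
|---|---|---|---|---|---|
| 0 | +1.5% | −0.6% | −3.2% | −12.1% | −18.9% |
| 2 | +4.5% | +2.4% | −0.3% | −9.4% | −16.4% |
| 4 | +7.8% | +5.6% | +3.1% | −6.6% | −13.5% |

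With none missing k = 1.015, so break-even is r = √(1 − 1/1.015²) = 0.17, or about 0.2. With 2 missing it is near 0.3, and with 4 missing between 0.3 and 0.5. CI coverage was 94.5–95.6% in every cell with or without the covariate, so omitting it causes no bias.

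**The case against.** The strongest reply is that no between-dose hypothesis exists. Each dose is tested separately against 50%, and describing onset at two doses is met by results per dose at each time. By-dose means and SDs are planned, the arms are independent, and a reader could form an unadjusted difference and CI by hand. The averaged CI does what it claims, and nothing in the SAP says it will be read as a 15-min effect. An early-only gap has no support in the documents. In the healthy-subject study, "At each dose level, peak %IPA was achieved within approximately" 15–30 min, and "The duration of PD effects was dose-dependent", which concerns duration and not onset. Normal PRU with SD 60 is also crude: if 85% of values lie below 100, many would be near the floor.

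Much of this stands. It limits the point to supportive analyses and makes the sizes illustrative. It does not remove the point, because the SAP itself chooses to model the between-dose difference over time, and the per-time contrasts come from the same data in the same model. Protocol 1.3 also says that AMI might affect uptake and onset, so the healthy-subject pattern is not assured here.

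SAP 6.8.2.2 says 60-min responder status will be analysed like the primary endpoint with the same factors. This could be read as including the logistic model with dose. Even so, it would compare responder status, not PRU.

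A reader might infer that the planned model is biased, or that the doses are known to differ in onset. The documents support neither.

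**Conclusion.** The point holds as a minor, inexpensive improvement. The SAP 6.8.2.2 model gives one valid time-averaged dose difference, and no planned analysis reports a between-dose PRU contrast with a CI at 15 or 60 min. Under the assumed inputs, how far this matters depends on the true pattern: substantial for a 30-PRU gap confined to 15 min, small for a 15-PRU gap, and nil if the difference is constant, where per-time contrasts cost precision.

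The baseline point at 30 min is weaker still. It is a precision question whose sign depends on an undocumented correlation.

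It would be wrong to infer any effect on the study's main conclusion. The primary responder tests, the 21 per arm and the success rule do not use these models, and Protocol 4.2 says the Phase 3 dose choice also draws on study ID-076A201.

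**What to change.** 1. In the SAP 6.8.2.2 model, add dose-by-time. Time is already listed by its three levels while other covariates are marked continuous, so only confirm that it is categorical.
2. Report the 8 mg versus 16 mg PRU contrast with 95% CI at 15, 30 and 60 min, alongside the averaged contrast. Interpret the contrasts and do not gate them on the interaction test.
3. Align baseline adjustment at 30 min, either by taking that contrast from the revised longitudinal model or by adding pre-dose PRU to the SAP 6.8.1.3 model.

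The cost is SAP wording and minor programming, with no new data. Dose-by-time uses 2 degrees of freedom, and the per-time CIs are wider than the averaged one, which is still reported. Pre-dose PRU in the 30-min model uses 1 degree of freedom. It also drops any mFAS subject without a pre-dose value, because the mFAS requires only the 30-min result (SAP 4.1.4), a missing baseline stays missing (10.2.2) and no imputation is planned (6.8.3). The longitudinal model already carries that restriction.
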